Four hundred fifty Veterans age 65-89 with CLBP, (for a targeted enrollment of 310), will be recruited from primary care provider (PCP) practices at 3 VAs – VA Pittsburgh Healthcare System, VA Greater Los Angeles, and Hunter Holmes McGuire (Richmond) VA. Individuals will be randomized to receive either ABC care or UC, and they will be followed for one year. Aging Back Clinics will be staffed by consultants (e.g., geriatrics, pain medicine, rheumatology) that have been trained in evaluating and treating key CLBP conditions associated with our published evidence-based algorithms. Usual care will not be constrained. Baseline measures will be assessed on site or on the telephone and include: Minimal Data Set recommended by the NIH Task Force on research standards for CLBP⁴; Oswestry Disability Index (ODI; main outcome)¹²; cognitive function (QMCI)¹³; PROMIS-29 that includes pain severity, pain-related activity interference, physical function, sleep disturbance, depressive symptoms, leg symptoms¹⁴; quality of life with the PROMIS-GH scale¹⁵, participant opioids-related concerns with the Prescribed Opioids Difficulties Scale¹⁶, gait speed, balance confidence with the Falls Efficacy Scale-International short form¹⁷; healthcare utilization over the prior month (e.g., pain medications, emergency room visits, hospitalizations) will be assessed on site. We will also be utilizing the Life Space Assessment¹⁰⁶ to measure the spatial extent of a participant's mobility. Three, 6-, up to 9-, and 12-months outcomes (ODI, PROMIS 29 and GH, balance confidence, healthcare utilization, life space assessment and VR-12) will be assessed over the telephone by individuals masked to group assignment. While monthly, the 0-10 Numerical Pain Rating Scale, Medications (pain medications monthly and all medications at baseline and final follow-up), and Health Care Utilization will be measured. The Global Impression of Change data measure will be administered only at the final phone follow up. The proposed clinical trial has the potential not only to improve pain-related disability, but also to reduce morbidity, increase quality of life, and limit healthcare utilization.

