Follow-up (Appendix 13): Quarterly telephone calls for up to 12 months following randomization will collect data on the main outcomes measure (the ODI) as well as the PROMIS 29, PROMIS-GH, VR-12, falls and falls efficacy (Falls Efficacy Scale-international short form), and the Life Space Assessment.¹⁰⁶ Health care utilization that includes pain medication use (oral morphine equivalents⁸⁷), emergency room visits, hospitalizations, and pain provider/other health care utilization as well as the 0-10 Numerical Pain Rating Scale will be collected monthly using established methods.⁹⁷ Monthly collection of data on health care utilization will facilitate comparison of key components of ABC care and Usual Care. During the final call at 12 months, the Perceived Intervention Value data measure will be administered as well as the Global Impression of Change data measure. Also, during the final call, all medications will be collected. To ensure the RC collecting these measures is masked to randomization group we will employ methodology that we have used successfully with other VA trials. For Example: the RC at the Pittsburgh site will collect follow up data on participants from the Los Angeles site, the RC from the Richmond site will collect follow up data on participants from the Pittsburgh site, and the RC from the Los Angeles VA will collect follow up data on participants from the Richmond site. Participants who were randomized to the UC group will be made aware that they may see an ABC provider at their site, outside of the context of this study, for one visit after completion of participation. Participants who were randomized to the ABC Care group will be contacted at their final month of participation, whether by phone, or if they choose on site, to discuss care after their participation. No data measures will be collected and no study related procedures performed. The ABC Providers will fill out a Final MD ABC Participant Assessment for each ABC Participant upon completion of their up to 12-month participation. The purpose of this data measure is for the provider to comment on each condition for which the participant was treated, and if the condition was in fact treated, and if not the rationale for not treating the condition. If during telephone-based follow up data collection (for a participant based at the sister site) the Veteran expresses suicidal ideations, the RC will ask the Veteran to hold on and (s)he will immediately call the site PI at the sister site (i.e., the site of the Veteran's home VA) who will call the Veteran and follow the facility's Suicide Threat Call Protocol. If the sister site PI is not immediately available, the RC will call the PI at their own site who will

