Perceived Intervention Value			final month
Global Impression of Change			final month

below. All statistical analyses will be performed using SAS® version 9 (SAS Institute, Inc., Cary, North Carolina) by the study statistician [name]. Participant flow will be summarized using a CONSORT diagram.⁹⁸ Data will be summarized by intervention arm and time point as well as baseline to follow-up change using appropriate descriptive statistics. First, the baseline participant characteristics will be compared between the two arms. Any significant differences will be noted and accounted for as covariates in the sensitivity analyses. Second, primary and secondary analyses to address the aims will be performed as outlined below using multiple imputation for missing data. The primary analysis will be performed to test the primary hypotheses H1.1 about the ODI. Secondary analyses will be performed for remaining hypotheses, secondary outcomes and other exploratory analyses. Third, we describe below our primary approach to missing data and a set of sensitivity analyses by including additional covariates, ignoring missing data, and reasonable alternative statistical modeling strategies to assess the robustness of our findings.

Baseline Comparison:

Due to the large sample size and the randomization scheme balanced with respect to site, it is highly unlikely that baseline participant characteristics will be significantly different between the arms. If we do find any, they will be included as covariates in the sensitivity analyses. We will not alter the primary analysis to preserve its a priori nature and predictability. We will use independent samples t- or Wilcoxon rank sum tests, as appropriate based on distributional properties, to compare continuous baseline characteristics between the intervention arms. For categorical baseline participant characteristics, we will use chi-square and Fisher's exact tests, as appropriate. Statistical significance of the intervention term will be interpreted as indicating the need to include them as covariates in sensitivity analyses.

Aim 1 Primary Analysis:

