We will fit a linear mixed model with baseline to follow-up change in ODI score as the dependent variable; intervention arm (ABC/UC), follow-up time point (6/12 months) and their interaction as fixed effect of main interest; baseline ODI as a fixed effect covariate; and a participant random effect to account for multiple repeated assessments of the same participant over time. The statistical significance at $\alpha=0.05$ of the ABC vs UC means contrast at the 6-month point will serve as the formal test of the primary hypothesis H1.1. Upon confirming the H1.1 primary hypothesis, we will compute the number-needed-to-treat (NNT) as the reciprocal of the between-intervention difference in percentages of those showing a meaningful ODI improvement above its MCID.

Aim 1 Secondary Analyses:

To characterize the intervention actually received under ABC care, we will describe the conditions identified, further evaluations/initiated treatments and their responses recorded in the form that tracks response to treatment and additional management plans (see Appendix 12). We will employ the same analytic strategy described above for ODI (under primary analysis) for our secondary continuous outcomes pain severity, quality of life and falls efficacy. The statistical significance of the ABC vs UC means contrast at the 6- and 12-month points will serve as the formal tests of the secondary hypotheses H1.2.

Measures of healthcare utilization between 6 and 12 months in H1.3 (prescriptions/refills of opioids and inappropriate medications for elderly, invasive procedures, emergency room/hospital visits) are mostly in the form of counts. As such, we will fit a series of generalized linear models with each count utilization outcome as the dependent variable, a negative binomial distribution to account for any over dispersion and a logarithmic link function for the count outcome, actual person-time of exposure with opportunity for reporting utilization outcome as an offset, and intervention arm (ABC/UC) as the independent factor of interest. Intervention arm incident rate ratios and their statistical significances will constitute tests of H1.3.

Aim 2 Analyses:

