The goal is to explore whether ABC vs UC differences in improvement vary across participant subgroups of interest (effect modification). We will add each of the subgroups (based on baseline CLBP-associated disability, anxiety/ depression, mild cognitive impairment and obesity) and associated subgroup \times intervention group interaction effects as additional fixed effects in the above statistical models. Rigorous methodological guidelines for subgroup analyses require significant interaction effects for making conclusions of differential intervention effects in subgroups.⁹⁹ As such, we will first construct difference-in-difference type means contrasts representing the difference in ABC vs UC effects in different subgroups at each of the follow-up time points. If and only if the said interaction contrast is significant, we will estimate ABC vs UC differences and

their statistical significance within those subgroups.

Missing Data:

The best approach for handling missing data is to prevent it. We will use the methods described earlier to retain participants and prevent missing data. Despite our best efforts, missing data will occur. We will clearly document those with missing data and reasons in the CONSORT diagram, and compare those with missing data to complete data with respect to available data. Statistical guidelines for handling missing data recommend methods such as multiple imputation, which considers the uncertainty involved in imputing missing data.¹⁰⁰ Multiple imputation is arguably the best available objective method to analytically account for missing data under the ignorable or missing-at-random (MAR) assumption. Specifically, we will generate M=5 imputed values for each missing value, analyze the 5 datasets as though complete, and finally combine the results appropriately so that they reflect the uncertainty involved in imputation. SAS® MI and MIANALYZE procedures will be used. Other approaches to missing data, including the naïve approaches of ignoring the missing values and last-value-carried-forward (LVCF) will also be considered in sensitivity analyses and robustness of the results to using these approaches will be examined.

Sensitivity Analyses:

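### The primary ODI model is limited to months 6 and 12 although the ODI is collected quarterly, and the imputation plan does not commit to using the month-3 and month-9 scores

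*Combined protocol and SAP*

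**What the plan says.** **Model.** Section 5.6 (Aim 1 Primary Analysis) takes change in ODI as the outcome, with "intervention arm (ABC/UC), follow-up time point (6/12 months) and their interaction as fixed effect of main interest", plus "baseline ODI as a fixed effect covariate; and a participant random effect to account for multiple repeated assessments". The test of H1.1 is at 6 months: "The statistical significance at $\alpha=0.05$ of the ABC vs UC means contrast at the 6-month point will serve as the formal test".

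**Collection.** Section 5.5 (Follow-up) says: "Quarterly telephone calls for up to 12 months following randomization will collect data on the main outcomes measure (the ODI" and several other scales. Section 3.0 gives the same schedule: "Three, 6-, up to 9-, and 12-months outcomes (ODI, PROMIS 29 and GH", and so on. Table 7 also marks the ODI as three-monthly. None of these separates the arms.

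**Missing data.** The section 5.6 overview says that "primary and secondary analyses to address the aims will be performed as outlined below using multiple imputation for missing data". The Missing Data paragraph adds: "Specifically, we will generate M=5 imputed values for each missing value, analyze the 5 datasets as though complete". It assumes data are missing at random (MAR) and names the SAS procedures. It does not say which variables enter the imputation model or whether imputation is done by arm. Analyses that ignore missing values or carry the last value forward are sensitivity analyses.

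**Withdrawal.** Section 5.7 ends follow-up calls at withdrawal and keeps the data already collected for analysis, without saying how.

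**The concern.** Calls stop at withdrawal, so a participant who withdraws between months 3 and 6 has neither a 6-month nor a 12-month ODI. The model's time factor has no place for that person's month-3 score. Only the imputation step can bring it in, and the plan does not say that it will.

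Two things are at stake. The first is precision: month-3 change is likely to be correlated with month-6 change, and the data will already be in hand. The second is the MAR assumption behind the primary test. If dropout after month 3 depends on the month-3 response, MAR holds when that response is conditioned on and can fail when it is not. If the pattern also differs by arm, the 6-month contrast is biased.

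Different patterns by arm cannot be ruled out from the design. Only outcome assessors are described as masked (section 5.5). Usual-care (UC) participants are offered an Aging Back Clinics (ABC) visit only after completing the study. Withdrawal ends study treatment in the ABC arm but leaves usual care unchanged (section 5.7).

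**Working it through.** **Inputs from section 5.6 (Sample Size Justification):** SD of ODI change 18; difference 7; two-sided alpha 0.05; 310 randomized; dropout 15%; 280 completers; power 90%. Allocation is 1:1 (section 5.5).

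**Assumptions not in the documents:** correlation rho between month-3 and month-6 change given baseline, 0.5 to 0.8; share s of dropouts with a month-3 score, 50% to 100%; 18 used as the residual SD.

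**Step 1. Reproduce the plan's power.** SE = 18 × sqrt(4/N) and power = Φ(7/SE − 1.96).
- N = 280: SE = 2.151, 7/SE = 3.254, power 90.2%. The stated 90% reproduces.
- 15% dropout from 310 leaves 310 × 0.85 = 263.5, not 280 (280/310 implies 9.7% dropout). N = 263.5: SE = 2.218, 7/SE = 3.156, power 88.4%.

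**Step 2. Precision when dropout is unrelated to response.** Let n6 be the number with a 6-month score and n3 = n6 + s(310 − n6) the number with a month-3 score. The variance of the 6-month contrast with month 3 used, relative to not used, is (1 − rho²) + rho² × n6/n3. Effective N is n6 divided by that ratio.

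| n6 | s | rho | variance ratio | SE ratio | effective N | power without → with month 3 |
|---|---|---|---|---|---|---|
| 263.5 | 0.5 | 0.5 | 0.980 | 0.990 | 269.0 | 88.4% → 89.0% |
| 263.5 | 0.5 | 0.8 | 0.948 | 0.974 | 277.9 | 88.4% → 90.0% |
| 263.5 | 1.0 | 0.5 | 0.963 | 0.981 | 273.8 | 88.4% → 89.6% |
| 263.5 | 1.0 | 0.7 | 0.926 | 0.963 | 284.4 | 88.4% → 90.6% |
| 263.5 | 1.0 | 0.8 | 0.904 | 0.951 | 291.5 | 88.4% → 91.3% |
| 280 | 0.5 | 0.5 | 0.987 | 0.994 | 283.6 | 90.2% → 90.6% |
| 280 | 1.0 | 0.8 | 0.938 | 0.969 | 298.5 | 90.2% → 91.9% |

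Worked row (263.5, s = 1, rho = 0.7): 0.51 + 0.49 × 263.5/310 = 0.926; 263.5/0.926 ≈ 284.4.

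**Step 3. Bias when dropout depends on the month-3 response.** Simulated trials of 310 participants had a true 6-month difference of 7. All dropout came after month 3, through a logistic model on standardized month-3 response. Slope 1.0 is an odds ratio of 2.7 per SD; slope 0.5 is 1.6. Bias is for the 6-month contrast without month 3. A positive sign favours ABC. Ranges run over rho 0.5 to 0.8.

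| Dropout pattern | Bias without month 3 (points) |
|---|---|
| 15% in each arm, unrelated to response | about 0 |
| 15% in each arm, poor responders leave alike (slope 1.0) | about 0 |
| Poor responders leave in both arms, 20% UC and 10% ABC (slope 1.0) | −0.7 to −1.2 |
| 15% in each arm, only UC dropout depends on response (slope 1.0) | −1.2 to −1.9 |
| 15% in each arm, only ABC dropout depends on response (slope 0.5) | +0.6 to +1.1 |
| 15% in each arm, only ABC dropout depends on response (slope 1.0) | +1.2 to +1.9 |
| 20% UC and 10% ABC, only UC dropout depends on response (slope 1.0) | −1.5 to −2.5 |
| 15% in each arm, opposite directions: UC poor responders and ABC good responders leave (slope 1.0) | −2.4 to −3.8 |

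With month 3 used (arm-specific regression of month 6 on month 3), bias was within 0.1 point in every scenario.

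**The case against.** The strongest reply is that the plan does not exclude month 3. A reader might infer from the two-level time factor that an early dropout's month-3 response is thrown away and that H1.1 therefore loses power and is biased. The documents do not support that. The primary analysis runs on imputed data, so such a participant does enter the model, with imputed 6- and 12-month values. Whether month 3 informs those values depends on an imputation model that lists no variables at all. Silence is not exclusion, and this part of the objection stands.

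Three further points also stand. Restricting the model to the visits named in the hypotheses, and recovering other information through imputation, is a legitimate design. Carrying the last value forward would use a month-3 score, though only as a sensitivity analysis that the plan itself groups with naïve approaches. The bias is conditional: it is zero in the symmetric case and can take either sign, so it would be wrong to infer that it favours ABC.

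The objection does not remove the gap. No analysis in section 5.6 names the month-3 or month-9 ODI. Section 5.6 stresses that the primary analysis should be fixed and predictable, yet its imputation predictors are left to be chosen later.

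**Conclusion.** The concern holds as a gap in specification that is almost free to close. It is not a demonstrated loss in H1.1. The model omits two of the four collected ODI visits, and nothing commits the imputation to using them.

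If month 3 is left out of both, the cost in precision is minor: at 15% dropout, power is 88.4% rather than 89.0-91.3%; with the stated 280 completers it is 90.2% rather than 90.6-91.9%. The stronger reason to act is protection against bias. Against a 7-point target, bias is about zero when dropout acts alike in both arms. It is roughly 0.6 to 1.9 points in either direction when either the dependence or the dropout rate differs by arm, up to 2.5 in the scenario where both differ, and up to 3.8 when the dependence runs in opposite directions. With month 3 used it is about zero under MAR.

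These sizes rest on the assumed correlation, the timing of dropout and the dropout models, none of which the documents give. The bias scenarios place all dropout after month 3, which is the case where using that score helps most.

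**What to change.** Keep the 6-month ABC-UC contrast at two-sided alpha 0.05 as the test of H1.1, and write one of these into section 5.6:

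1. Fit all quarterly ODI visits (3, 6, 9 and 12 months) with time as a categorical factor, arm-by-time interaction, and an unstructured within-participant covariance. Adding visits under the random participant effect alone would force equal correlations between all pairs of visits.
2. Keep the 6/12-month model, and state that imputation is done separately by arm and includes baseline ODI and all quarterly ODI scores.

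Apply the same choice to the H1.2 outcomes collected quarterly, which follow the same analytic strategy. Settle it before any unblinded analysis, because predictors chosen afterwards would be open to challenge.

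The cost is a sentence or two of SAP text and minor programming. No new data are needed, and the endpoint, alpha and hypothesis are unchanged.

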Randomization and Blinding: Following baseline testing, we will use the high quality pseudo-random deviate generator in SAS® (SAS Institute, Inc., Cary, North Carolina) to randomize participants to ABC care or UC in a 1:1 ratio, stratified by recruitment site. Within each site, we plan a blocked randomization scheme to force continued approximate balance between the numbers of subjects in each arm during recruitment. The block size will be randomly chosen to be one of two small even numbers to prevent personnel from predicting treatment arm, and exact block sizes will be revealed at the study conclusion. The study statistician will create separate randomization schedules for the 3 strata that contains a randomization sequence number (different from a participant's study identification number) and assigned arm. Then he will create a series of sealed envelopes for each of the sites containing the treatment assignment but conspicuously labeled on the outside with only the randomization sequence number. At the time of randomization, the overall RC based at the coordinating site will open the next available envelope specific for the participant's site, and record the randomization sequence number, subject identification number and group assignment in a dedicated database, different from the main study database. She will then inform the RC at the participant's site of their randomization group and the local RC will inform the participant of next steps. Personnel assessing follow-up outcomes will be masked to intervention assignment (see Follow-Up below). The study statistician has successfully employed the same process in other clinical trials.

Intervention

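### Randomization is stratified by site, but no efficacy model contains site: if site predicts outcome, the tests are slightly conservative and a small gain in power is forgone

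*Combined protocol and SAP*

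**What the plan says.** Section 5.5 (Randomization and Blinding) states that the trial will "randomize participants to ABC care or UC in a 1:1 ratio, stratified by recruitment site". It adds: "The study statistician will create separate randomization schedules for the 3 strata". On blocking it says: "Within each site, we plan a blocked randomization scheme to force continued approximate balance".

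Section 5.6 (Aim 1 Primary Analysis) lists the terms of the ODI model: "intervention arm (ABC/UC), follow-up time point (6/12 months) and their interaction as fixed effect of main interest", then "baseline ODI as a fixed effect covariate; and a participant random effect to account for multiple repeated assessments". The H1.2 continuous outcomes are to be analysed in the same way. For the H1.3 utilization counts, the negative binomial model has a person-time offset and "intervention arm (ABC/UC) as the independent factor of interest". Site appears in none of these lists.

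The Aim 2 models add only subgroup terms. Under Baseline Comparison and Sensitivity Analyses, extra covariates are baseline characteristics that turn out to differ significantly between arms. Elsewhere in section 5.6, site is mentioned only as a reason to expect balanced arms. Baseline Comparison also says the primary analysis will not be altered afterwards.

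**The concern.** Forcing balance within each site takes between-site variation out of the true sampling variance of the arm difference. A model without site leaves that variation in its residual, so the reported standard error describes a less precise design than the one used. The interval is then too wide and the test runs below its nominal 5% level.

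The conditional covariate rule does not repair this. It is triggered by imbalance between arms, and stratification makes imbalance on site very unlikely.

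There is a plausible route to a site effect. Section 5.5 (Follow-up) gives, as an example, a scheme in which each site's follow-up calls are made by the coordinator of one other site, while baseline is collected by the local coordinator. The outcome is change from baseline, so a difference between interviewers would appear as a site difference in change. Usual care is also unconstrained and may vary locally. What is at stake is some precision in every efficacy comparison.

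**Working it through.** **Inputs from section 5.6 (Sample Size Justification and Statistical Power).** Difference 7 ODI points; SD of change 18; two-sided alpha 0.05; power 90%; 310 randomized; 280 completers. The same paragraph gives 15% dropout, which leaves 310 × 0.85 = 263.5, about 264. That mismatch is a separate matter, but both completer counts are used below.

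**Plan's own figure.** With n per arm, SE = 18 × √(2/n). For n = 140, SE = 2.151 and power = Φ(7/2.151 − 1.96) = 90.2% (90.0% with the noncentral t). The stated 90% is reproduced.

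**Assumption.** R² is the share of outcome variance explained by site. The documents give no value, so a range is shown. With total SD 18, R² of 0.02, 0.05 and 0.10 corresponds to a between-site SD of 18 × √R² = 2.5, 4.0 and 5.7 ODI points.

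**Formulas, arms balanced within site.**
- Reported SE without site: SE_m = 18 × √(2/n)
- True SE: SE_t = SE_m × √(1 − R²)
- Actual type I error without site: 2 × [1 − Φ(1.96/√(1 − R²))]
- Power without site: Φ((7 − 1.96 × SE_m)/SE_t)
- Power with site: Φ(7/SE_t − 1.96)

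**Worked case, R² = 0.05, n = 140.** SE_t = 2.151 × √0.95 = 2.097. Type I error = 2 × [1 − Φ(2.011)] = 4.4%. Power without site = Φ((7 − 4.217)/2.097) = 90.8%. Power with site = Φ(7/2.097 − 1.96) = 91.6%.

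| R² | Reported SE too large by | Type I error without site | Power without / with site, 280 completers | Power without / with site, 264 completers |
|---|---|---|---|---|
| 0 | 0% | 5.0% | 90.2 / 90.2% | 88.5 / 88.5% |
| 0.02 | 1.0% | 4.8% | 90.4 / 90.8% | 88.7 / 89.1% |
| 0.05 | 2.6% | 4.4% | 90.8 / 91.6% | 89.1 / 90.0% |
| 0.10 | 5.4% | 3.9% | 91.4 / 92.9% | 89.7 / 91.5% |

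Before rounding, the power forgone at R² = 0.02, 0.05 and 0.10 is 0.3, 0.8 and 1.6 points with 280 completers, and 0.4, 0.9 and 1.8 points with 264.

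**Simulation check.** Three sites, permuted blocks of 2 or 4, 280 completers, 8,000 runs per setting, least squares at one time point. At R² = 0.10 without site, the mean reported SE was 2.15 against an empirical SD of 2.01 to 2.04; type I error was 3.9% and power 91.6%. With site, type I error was 4.9% and power 93.0%. This agrees with the closed form.

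**Count models, illustration only.** Assumed mean 0.5, dispersion 1, rate ratio 0.6, 280 participants, 600 runs. With site log-rates in steps of 0.3, power was 61.0% without site and 60.8% with it. With steps of 0.7, it was 58.7% and 62.2%.

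**The case against.** The strongest reply is that the effect is conditional, small and on the safe side. It vanishes if site does not predict ODI change after baseline adjustment, and the documents offer no evidence that it does. Within the range shown it stays below 2 points of power. A positive H1.1 result from the planned model would stand. The calculation is also simpler than the planned analysis, which is a mixed model over two time points with baseline ODI and multiple imputation; baseline ODI may already absorb part of any site difference. All of this stands, and it limits the weight of the point. It does not remove the mismatch between allocation and analysis.

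Four stronger readings are tempting, and the documents do not support them:
- A reader might infer that the stated 90% power is eroded. The SD of 18 is given as the between-subject SD of change, with no mention of site adjustment. Read as the total SD, it yields 90.2% with no site term and no site effect. In the table, power without site never falls below the R² = 0 value for the same completer count.
- A reader might cite the separate ABC providers at each site as a source of the problem. They act only in the ABC arm, so any difference would be mainly a site-by-arm effect, which a site main effect does not model.
- A reader might assume the same gain for H1.3. The illustration shows none at moderate site differences and about 3.5 points only at large ones.
- A reader might conclude that the imputation model omits site. Section 5.6 (Missing Data) does not list the imputation variables, so this is not established.

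**Conclusion.** The omission of site from the H1.1, H1.2 and H1.3 models is certain from the text. Its consequence is conditional and minor. If site explains 2 to 10% of the variance in ODI change, the reported standard error is 1 to 5% too large, the nominal 5% test operates at about 4.8 to 3.9%, and some 0.3 to 1.8 points of power for H1.1 are forgone across the two completer counts. If site explains nothing, nothing is lost. Validity is not threatened. The figures rest on an assumed site share of variance, a total SD of 18, near-exact balance within site and a single-time-point approximation. The point merits action because the correction is nearly free, not because the trial is at risk without it.

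**What to change.** In section 5.6, add recruitment site (three levels) as a prespecified fixed effect to the H1.1 mixed model, to the H1.2 models that follow it, and to the H1.3 negative binomial models. State that site is also in the imputation model, so that imputation and analysis match. Make the change before outcome data are examined by arm, because the plan commits to leaving the primary analysis unaltered. If wanted, keep the model without site as a sensitivity analysis.

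The cost is two degrees of freedom and one term per model; nothing changes in the conduct of the trial. For the count models the gain may be negligible unless utilization differs widely between sites, and the main reason to include site there is consistency with the randomization.
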